5.2 Study Flow Diagram

### 5.3 Methods to Reduce Bias

(1) **Standardized data collection** – All data extractors at participating centers will receive uniform training. Standardized Case Report Forms (CRFs) will clearly define each variable (e.g., “positive margin” defined as tumor cells present at the margin on pathology; “local recurrence” requires pathological confirmation) to reduce measurement and information bias.

(2) **Double independent extraction of key variables** – For primary outcome variables (recurrence, metastasis, death) and key exposure variables (pathological grade, surgical procedure, margin status), two researchers will independently extract data and cross-validate. Discrepancies will be adjudicated by a third senior researcher.

(3) **Clear inclusion/exclusion criteria** – Strict definitions will avoid selection bias. All eligible consecutive cases will be enrolled; no sampling based on outcome or exposure.

(4) **Handling of missing data** – Cases with >20% missing key variables will be excluded. For variables with  $\leq 20\%$  missingness, multiple imputation ( $m=5$ ) will be used. Results from complete case analysis and imputed analysis will be compared to assess missingness bias.

(5) **Confounding control** – Multivariable regression models will adjust for known prognostic factors (age, tumor size, pathological grade, margin status, etc.). For non-randomized treatment comparisons (e.g., different surgical procedures), propensity score matching (PSM, caliper =  $0.2 \times \text{SD of PS}$ ) or inverse probability of treatment weighting (IPTW) will be used to balance covariates. E-values will be calculated to evaluate the strength of unmeasured confounding.

(6) **Control of multicenter heterogeneity** – Center effects will be adjusted using Cox shared frailty models or generalized estimating equations (GEE) with center as a random effect.

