### **(5) Bias control (as described in 5.3) – PSM, IPTW, E-value.**

### **(6) Stratified, subgroup, and sensitivity analyses**

- **Stratified analysis:** All primary analyses will be stratified by pathological grade (benign/borderline/malignant) to compare prognostic factors across grades.
- **Pre-specified subgroups:** Age (<35 vs. ≥35 years), tumor size (<5 cm vs. ≥5 cm), surgical procedure (segmental resection vs. minimally invasive rotary

excision, wide local excision vs. total mastectomy). Forest plots will display subgroup HRs with interaction P-values.

- **Sensitivity analyses:**
  - Complete case analysis vs. multiple imputation.
  - Varying PSM parameters (1:1 vs. 1:2 matching, caliper 0.1 vs. 0.2).
  - Separate analysis of recurrence definitions (ipsilateral chest wall/axilla only) to exclude misclassification.
  - Excluding patients with follow-up <6 months.
  - For OS, competing risk analysis with death from PT vs. other causes.

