### **6.2.3 Data Integrity Checks**

- **Source Data Verification (SDV):** The project team will randomly select 10% of cases. A quality control officer will compare the data in the eCRF with the original hospital electronic medical records item by item to ensure transcription accuracy.
- **Logical Checks:** Logic validation rules will be embedded at the database design stage (e.g., surgery date cannot be later than recurrence date; tumor size cannot be negative). The system will automatically flag data points that violate logic, requiring mandatory review.
- **Missing Value Management:** The system will generate regular missing value reports. For critical variables (e.g., pathological grade, surgical margin status, follow-up outcomes), every effort will be made to trace back to medical records for supplementation. If supplementation is truly impossible, the value will be clearly recorded as "missing" and its impact will be assessed in subsequent statistical analyses.

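### Comparing complete-case with imputed results cannot detect value-dependent missingness in margin status, so agreement between them can give false reassurance

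*Combined protocol and SAP*

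**What the plan says.** Section 5.3(4) sets three steps. Heavily incomplete records are dropped: "Cases with >20% missing key variables will be excluded". For variables with at most 20% missing, "multiple imputation ( $m=5$ ) will be used". Then: "Results from complete case analysis and imputed analysis will be compared to assess missingness bias".

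The sensitivity analyses in section 5.4.2(6) contain one item on missing-data handling, "Complete case analysis vs. multiple imputation", which is the same comparison.

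Section 6.2.3 counts surgical margin status among the critical variables for which "every effort will be made to trace back to medical records for supplementation". Where that fails, the value is recorded as missing and "its impact will be assessed in subsequent statistical analyses". It does not say how.

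The documents do not state a missing-at-random assumption, specify the imputation model or plan a missing-not-at-random analysis. The E-values in section 5.3(5) address unmeasured confounding, not missing data.

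**The concern.** Multiple imputation in its standard form draws each missing margin from the distribution seen in patients whose margin was recorded, given the other variables. If unrecorded margins differ systematically from recorded ones, the imputed values reproduce the recorded pattern. The complete-case analysis uses that same pattern directly. Both estimates can therefore be wrong by the same amount, and comparing them would not show it.

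Margin status has several roles in the plan. It is a key exposure (5.3(2)), an adjustment factor (5.3(5)), a secondary endpoint (3.2.2(12)) and part of the treatment-pattern objective (3.1.2(2)). Section 2.2.3 calls the optimal margin width controversial, and the abstract offers the study in support of guideline updates. Both the positive-margin rate and the margin hazard ratio are likely to be cited, so a check that cannot detect this bias should not be presented as an assessment of it.

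**Working it through.** **The plan's own figure.** Section 5.4.1 expects about 380 recurrences. 3,500 × 0.11 = 385. Weighting the grade-specific rates in section 2.2.2 by the 7:2:1 mix gives 0.7 × 7.1% + 0.2 × 16.7% + 0.1 × 25.1% = 10.82%, and 3,500 × 0.1082 = 379. The figure reproduces and is not in dispute.

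**Inputs.** From the documents: 3,500 patients, about 11% recurrence, the grade mix, m = 5, and imputation of variables up to 20% missing. Assumed, because the documents do not give them: 15% positive margins, a true hazard ratio (HR) of 1.5, about 20% of margins missing, and every missingness pattern below.

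**Positive-margin rate, missingness depending on margin alone** (positives missing in 30%, negatives in 18%).
- Recorded positives: 0.15 × 0.70 = 0.105. Recorded negatives: 0.85 × 0.82 = 0.697.
- Overall missing: 1 − 0.802 = 19.8%.
- Complete-case rate: 0.105 / 0.802 = 13.1%, against a true 15%. Standard imputation fills the gaps at about the same rate, so it also reads about 13%.

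**Margin effect.** Write p(x,y) for the probability that the margin is missing, where x = 1 is a positive margin and y = 1 is recurrence. Then

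observed odds ratio = true odds ratio × [(1 − p(1,1)) × (1 − p(0,0))] / [(1 − p(1,0)) × (1 − p(0,1))].

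If p depends on margin alone or on recurrence alone, the factor is 1. It can depart from 1 only when p depends on both. An imputation model fitted to the recorded cases inherits the same odds ratio.

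A logistic simulation checked this: 3,500 patients, 400 repetitions, true odds ratio 2.0, about 14.5% positive margins, imputation from recurrence and grade.

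| Missing margins | Formula | Complete-case / imputed |
|---|---|---|
| Completely at random, 20% | 2.0 | 2.01 / 2.01 |
| Recurrence alone (22% without, 5% with) | 2.0 | 1.99 / 1.99 |
| Margin alone (positives 37%, negatives 17%) | 2.0 | 1.99 / 1.99 |
| Positives 30% without and 15% with recurrence; negatives 19% | 2.0 × 0.85/0.70 = 2.43 | 2.43 / 2.43 |
| Positives 40% without and 10% with recurrence; negatives 17% | 2.0 × 0.90/0.60 = 3.00 | 2.98 / 2.98 |
| Reverse: positives 10% without and 40% with; negatives 20% without and 10% with | 2.0 × (0.60 × 0.80)/(0.90 × 0.90) = 1.19 | 1.17 / 1.17 |

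In the last three rows the two estimates lay within half a standard error of each other in 99–100% of repetitions, while coverage of the nominal 95% interval fell to between 7% and 74%. Under missing completely at random they agreed equally closely (99%). In the margin-alone row the positive-margin rate read 11.5% in both analyses, against 14.5%.

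**Cox version** (true HR 1.5, complete-case / imputed, separate simulation runs).
- Positives missing in 10% with recurrence and 30% without, negatives about 19–20%: 1.83/1.83, 1.86/1.86 and 1.88/1.88. The odds-ratio factor is 0.90/0.70 = 1.29. The HR moves slightly less because recurrence is not vanishingly rare.
- Positives 20% with and 25% without: 1.60/1.59.
- Margin alone, 30% against 18%: 1.50/1.49 and 1.53/1.53.
- Recurrence alone, 10% with against 21% without: 1.45/1.46.
- Completely at random: 1.48/1.48 and 1.49/1.49.

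**Would a delta adjustment reach these cases?** The multiplier needed on the imputed odds of a positive margin is the odds of being missing for positives divided by that for negatives. In the margin-alone example it is (0.30/0.70) / (0.18/0.82) = 1.95 in both recurrence groups. In the 10%-versus-30% pattern, with negatives at 19.5%, it is (0.10/0.90) / (0.195/0.805) = 0.46 with recurrence and (0.30/0.70) / (0.195/0.805) = 1.77 without. A single common shift would miss the second pattern, so the shift must vary by recurrence status.

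**The case against.** The strongest objection concerns mechanism. A reader might infer that patients who recur have more records, that their margins are more often recovered, and that the margin HR is therefore inflated. The documents do not support that. Fuller records help to recover negative margins as well as positive ones, and recovery that depends on recurrence alone leaves the HR near 1.5, as shown above. Even if positives are harder to recover and recurrence helps both groups (positives 30% down to 10% missing, negatives 20% down to 7%), the simulated HR is 1.64/1.65. Values of 1.8 to 1.9 need a specific margin-by-recurrence interaction that nothing in the documents establishes. This objection stands, and those values are a worst-case illustration only.

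The plan also has safeguards. Data entry staff are blinded to recurrence and metastasis while entering clinical and pathological data (6.2.4). Margin status is extracted twice, independently (5.3(2)). The pathology information system is a source (6.1.2), so finding the index report need not depend on later visits. These lower the risk. They do not enable the comparison to detect the bias if it occurs.

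The plan says only that results will be compared, not that agreement proves absence of bias, and identifying prognostic factors is an exploratory objective (3.1.3(2)). Both are fair. The stated purpose is still to assess missingness bias, and no other missing-data analysis is named.

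Finally, margin status might never be imputed. Section 4.2(3) excludes patients with missing critical data, and its examples omit margin status; section 6.2.3 calls margin status critical. If such patients are excluded, the comparison cannot address margin missingness at all.

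**Conclusion.** The concern holds in a limited form. Agreement between complete-case and imputed results does not separate sound data from value-dependent missingness, so it can give false reassurance; it does not always do so. With positives missing in 30% and negatives in 18%, the positive-margin rate reads about 13% instead of 15% in both analyses. The margin HR is at risk only under joint dependence on margin and recurrence, and the error may go in either direction.

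A reader might go further and infer that the planned margin HR will be biased, or that any value-dependent missingness biases it. Neither follows: missingness by margin alone left the HR at about 1.5. Margin prevalence, the true HR, the missingness rates and their patterns are all assumed, and 20% missing is the plan's ceiling for imputation, not an expected rate. The comparison keeps some use, because a difference between the two results would show sensitivity to the handling method.

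**What to change.** 1. In sections 5.3(4) and 5.4.2(6), keep the comparison but describe it as a check of sensitivity to the handling method under missing at random, and state that assumption. Do not call it an assessment of missingness bias.
2. Add a delta-adjusted (tipping-point) multiple imputation for margin status in mice, which section 5.4.2 already lists. Shift the imputed log-odds of a positive margin over a prespecified range, separately for patients with and without recurrence. Report the shift at which the conclusion on the positive-margin rate or the margin HR changes. The range is the study team's choice; the multipliers derived above (about 0.46 to 1.95) show what it would need to cover for those illustrative patterns.
3. Reconcile sections 4.2(3) and 6.2.3 on whether patients with missing margin status are excluded or imputed. Item 2 applies only if they are imputed.

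The cost is SAP wording and a few extra imputation runs, with no new data. The downside is a possibly more cautious conclusion about margins.

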**3.2.2 Secondary Endpoints and Definitions**

**(1) Age at diagnosis** – Age (in years) when the patient was first diagnosed with breast PT.

- (2) **Menstrual status** – Premenopausal or postmenopausal.
- (3) **Childbirth history** – Yes or no.
- (4) **Family history of malignant tumors and PT** – Includes family history of breast cancer, other malignant tumors, and PT. Categorized as yes or no.
- (5) **Previous fibroadenoma surgery** – History of breast surgery for fibroadenoma. Categorized as yes or no.
- (6) **Maximum tumor diameter** – Largest tumor dimension (in cm) measured by preoperative imaging (ultrasound, etc.).
- (7) **Multifocality** – Solitary or multiple ( $\geq 2$  lesions in the same breast).
- (8) **Tumor location** – Left breast, right breast, or bilateral.
- (9) **Imaging findings** – Descriptions from breast and axillary ultrasound, mammography, breast MRI, chest CT, PET-CT, etc. (e.g., lobulated shape, margins, vascularity).
- (10) **Histological grade** – Benign, borderline, or malignant according to WHO criteria.
- (11) **Surgical procedure** – Type of initial surgery: wide local excision, total mastectomy, mastectomy with reconstruction, breast-conserving surgery, etc.
- (12) **Margin status** – Whether tumor cells are present at the surgical margin on postoperative pathology: negative (no residual tumor) or positive (residual tumor present). Margin distance (in cm) is also recorded.
- (13) **Adjuvant chemotherapy** – Whether adjuvant chemotherapy was given after surgery (yes/no), with details of regimen if available.
- (14) **Adjuvant radiotherapy** – Whether adjuvant radiotherapy was given after surgery (yes/no), with details of regimen if available.
- (15) **Axillary biopsy report** – Whether axillary lymph node biopsy (sentinel lymph node biopsy or axillary lymph node dissection) was performed, and the total number of lymph nodes examined and number of positive nodes recorded.

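### Margin status, a result of the operation, is an adjustment factor and is not excluded from the surgical comparisons, so a procedure hazard ratio may not be the total effect; re-excision is not handled

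*Combined protocol and SAP*

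**What the plan says.** Section 5.3 (5), on confounding control, makes two statements. On regression it says: "Multivariable regression models will adjust for known prognostic factors (age, tumor size, pathological grade, margin status, etc". On treatment contrasts it says: "For non-randomized treatment comparisons (e.g., different surgical procedures), propensity score matching", with the alternative that "inverse probability of treatment weighting (IPTW) will be used to balance covariates". Those covariates are not named.

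Section 5.3 (2) places both variables among the "key exposure variables (pathological grade, surgical procedure, margin status". Section 5.4.2 (3) enters the secondary endpoints, which include procedure and margin, as covariates in Cox or logistic models for the primary outcomes. Section 5.4.2 (4) selects variables by backward AIC or LASSO.

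Section 3.2.2 (11) defines procedure as "Type of initial surgery: wide local excision, total mastectomy, mastectomy with reconstruction, breast-conserving surgery, etc". Section 3.2.2 (12) defines margin as "Whether tumor cells are present at the surgical margin on postoperative pathology: negative (no residual tumor) or positive (residual tumor present", without saying which specimen counts when there is more than one. Section 3.2.1 (3), (7) and (9) start the clock at the initial operation. No variable, rule or sensitivity analysis in 5.4.2 (6) deals with re-excision or completion mastectomy. One surgical subgroup contrast there is "segmental resection vs. minimally invasive rotary" excision, and the list in 3.2.2 (11) names neither procedure.

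**The concern.** A confounder of the choice of operation has to come before it. Margin status comes after it and depends partly on how much tissue was removed, so it lies on the path from procedure to local recurrence. Conditioning on it removes that part of the procedure effect. What remains is a direct effect at best, and only if nothing unmeasured drives both margin and recurrence. The plan does not distinguish the two quantities. Automated selection adds a risk: if procedure acts mainly through margin, AIC or LASSO may drop procedure, and the report would then say that procedure does not matter.

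The second problem is one of measurement. A patient who has a local excision and soon afterwards a re-excision or completion mastectomy is classified by the first operation. If her margin is also taken from the first specimen, a cleared margin is counted as positive and the margin HR is pulled towards 1.

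Section 2.2.3 presents margin width as controversial, and 3.1.3 (2) wants the prognostic results to inform treatment decisions. Either error would bear on that use. The planned E-values address unmeasured confounding; they detect neither adjustment for a mediator nor misclassified exposure.

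**Working it through.** **1. The plan's own figure.** Section 5.4.1 expects about 380 recurrences: 3,500 × 0.11 = 385. From the 7:2:1 grade mix and the recurrence rates in section 2, (7 × 7.1% + 2 × 16.7% + 1 × 25.1%)/10 = 10.82%, and 3,500 × 0.1082 = 379. The figure reproduces. With 30 to 40 variables it gives 380/30 = 12.7 to 380/40 = 9.5 events per variable, so procedure and margin can easily sit in one model. This point disputes no figure in the plan.

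**2. Where margin can enter a procedure estimate.**
- Multivariable models: margin is a named adjuster in 5.3 (5), and 5.4.2 (3) enters procedure as a covariate too. A procedure HR from such a model is conditional on margin.
- Propensity-score matching or weighting: no covariate list. Margin is neither included nor excluded.

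**3. Effect on the procedure HR (illustration; all inputs assumed).** Suppose procedure acts only through margin. Positive margins occur in a proportion pw after local excision and pm = 0.05 after mastectomy, and the recurrence HR for a positive margin is h. As a ratio of average hazards, mastectomy versus local excision:

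Total HR = [(1 − pm) + pm·h] / [(1 − pw) + pw·h]

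- pw = 0.20, h = 2: (0.95 + 0.10)/(0.80 + 0.40) = 1.05/1.20 = 0.875
- pw = 0.30, h = 3: (0.95 + 0.15)/(0.70 + 0.90) = 1.10/1.60 = 0.69

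Within margin strata the HR is 1.00 by construction.

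Simulated Cox models (150,000 patients per scenario, equal allocation, censoring uniform over 2 to 20 years) agree. In the reverse direction, local excision versus mastectomy:

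| Positive margins | Margin HR | Total procedure HR | Margin-adjusted procedure HR |
|---|---|---|---|
| 15% vs 5% | 2 to 4 | 1.08 to 1.21 | 0.98 to 1.00 |
| 25% vs 5% | 2 to 4 | 1.18 to 1.45 | 0.99 to 1.00 |
| 30% vs 2% | 2 to 4 | 1.25 to 1.71 | 0.98 to 1.00 |

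In these runs the margin HR itself is recovered with procedure in the model (for example 3.07 when the truth is 3). In one further run, an unmeasured factor drove both margin and recurrence; the margin-adjusted procedure HR was then 0.92 although the true direct HR was 1.0. The conditional estimate is therefore not automatically a clean direct effect.

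**4. Effect of first-specimen coding on the margin HR (illustration; assumed inputs).** If a fraction c of initially positive margins is cleared by further surgery and cleared patients carry no excess risk, the apparent HR is about (1 − c)·h + c.

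- h = 2.5, c = 0.5: 0.5 × 2.5 + 0.5 × 1 = 1.75
- h = 3, simulated: c = 0.3, 0.5 and 0.7 give 2.35, 2.00 and 1.54. Coding the final margin returns 2.96 to 3.06.

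**The case against.** The best defence is that 5.3 (5) keeps the two tasks apart: margin is listed for the multivariable models, while surgical comparisons go to matching or weighting. Section 3.1.3 (2) sets out to screen independent prognostic factors, and margin is a proper predictor there. No section names the total causal effect of procedure as an objective, so a margin-conditional HR misleads only if it is read as that effect.

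Much of this stands, and it limits the point in four ways.
- A reader might infer that the plan adjusts the surgical comparisons for margin. It does not say so; it only fails to rule it out.
- A reader might infer that joint adjustment also biases the margin HR. It does not: procedure is a confounder of the margin effect and belongs in that model. Any dilution would come from specimen coding and untracked re-excision.
- A reader might infer that the first-specimen margin is used. Section 3.2.2 (12) leaves this open, and if the final margin is recorded the dilution in step 4 does not arise.
- The procedure list in 3.2.2 (11) is open-ended, and 6.2.4 promises a data dictionary. The mismatch with the subgroup categories is a wording matter to reconcile, not a source of bias.

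The defence does not remove the gap. The only covariates that 5.3 (5) names include margin, the heading is confounding control, and the plan compares procedures as exposures without saying which effect it reports.

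**Conclusion.** The point holds in this form. A procedure HR from the multivariable models would be conditional on a result of the operation, and the plan does not prevent the same in the propensity-score comparisons. Such an HR is not the total effect of procedure and can conceal a real difference. Separately, coding only the initial operation, with the margin specimen undefined and no rule for re-excision, leaves the margin HR open to dilution.

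The sizes are illustrations: a total HR of about 0.69 to 0.87 moving to about 1.0, and a margin HR of 2.5 appearing as about 1.75. They rest on assumed margin-positivity, margin-effect and re-excision figures, and the 1.0 follows from assuming that procedure acts only through margin. The documents supply none of these inputs, so neither size nor direction can be fixed for this cohort. The statement that the plan's procedure and margin estimates are both biased as written goes further than the text supports.

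**What to change.** - **Procedure comparisons** (matching, weighting and the corresponding Cox models): list the covariates. Use pre-operative factors plus grade, centre and calendar period; leave out margin status and adjuvant therapy. Grade is read on the specimen but describes the tumour rather than the operation, so it stays.
- **Prognostic-factor models:** keep margin, and label any procedure HR from them as conditional on margin.
- **Data definitions:** record re-excision and completion surgery with dates, from existing records. Define margin at the final specimen of the primary surgical treatment.
- **Sensitivity analysis:** classify procedure by the definitive operation. Keep the primary time zero at the initial operation, as 3.2.1 (3), (7) and (9) state. This classification uses information from shortly after time zero, which is why it is offered as a sensitivity analysis. A landmark start would change the defined endpoints and is not needed for this point.
- **Wording:** reconcile the procedure list in 3.2.2 (11) with the subgroup categories in 5.4.2 (6).

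The cost is SAP wording, a few extra data fields and one additional analysis. The expected number of events does not change.

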## **2.2 Current State of Research – Domestic and International**

### **2.2.1 Clinicopathological Features**

International research on breast PT began early. As early as 1774, this rare tumor was described as a "giant fibroadenoma" [10]. In 1838, Johannes Muller first used the term "cystosarcoma phyllodes" to describe PT, characterizing it as a sarcoma-like lesion with a cystic, leaf-like cut surface, rapid clinical growth, and large size. In 1981, the WHO adopted the term "phyllodes tumor" and defined it as "a rare fibroepithelial neoplasm with a leaf-like structure, composed of breast fibrous connective tissue and epithelial components" [11]. With deeper understanding of PT features, the 2019 WHO three-tier classification (benign, borderline, malignant based on tumor borders, stromal cellularity, stromal atypia, mitotic count, stromal overgrowth, and malignant heterologous elements) has become the internationally accepted diagnostic standard [12].

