## **5. Study Design**

### **5.1 Overall Design**

[figure not shown]
This is a multicenter, retrospective cohort study. Data will be collected from patients who underwent breast surgery at the Departments of Breast Surgery of the following eight participating centers between January 1, 2001, and December 31, 2023:

- Sun Yat-sen Memorial Hospital, Sun Yat-sen University
- The First People's Hospital of Foshan
- Sun Yat-sen University Cancer Center
- Peking University Shenzhen Hospital
- Foshan Women and Children's Hospital
- The First Affiliated Hospital of Guangzhou Medical University
- Zhongshan People's Hospital
- Shanwei People's Hospital

The expected sample size is approximately 3,500 patients. Using real-world data over nearly 20 years, the study will systematically describe the clinicopathological characteristics, treatment patterns, and long-term prognosis of breast PT in China, and identify independent risk factors through descriptive analysis, propensity score methods, competing risk models, and sensitivity analyses.

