##### **(1) Descriptive analysis**

- **Demographic and clinicopathological characteristics:** Continuous variables will first be tested for normality (Shapiro-Wilk test). Normally distributed variables will be presented as mean  $\pm$  SD, with group comparisons using t-test or ANOVA; non-normally distributed variables as median (IQR), with group comparisons using Mann-Whitney U or Kruskal-Wallis test. Categorical variables as frequency (%), with group comparisons using Pearson  $\chi^2$  test or Fisher's exact test (when expected frequency  $<5$ ).
- **Treatment patterns:** Distributions and temporal trends (e.g., by 5-year intervals) of surgical procedures, margin status, lymph node surgery, and adjuvant radiotherapy/chemotherapy will be described, stratified by pathological grade and time period.
- **Outcome events:** Local recurrence rate, distant metastasis rate, and tumor-specific mortality rate will be calculated for the overall cohort and by pathological grade. Time to recurrence, number of recurrences, and proportion/probability of grade progression after recurrence will be described.

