### **(4) Statistical adjustments**

- Multivariable model variable selection: backward stepwise regression (based on AIC) or LASSO penalized regression (when many variables).
- Proportional hazards assumption: tested using Schoenfeld residuals. If violated, stratified Cox, time-dependent covariates, or accelerated failure time models will be used.
- Multiple comparisons: For three primary endpoints (LR, DM, OS), each will be analyzed separately without multiple correction. For multiple exposure comparisons within the same endpoint, Bonferroni correction will be applied.

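### Centre adjustment offers a GEE with a random effect, which is not a model and does not fit the censored endpoints or 8 centres; separately, year of surgery is never named as an adjuster over 2001–2023

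*Combined protocol and SAP*

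**What the plan says.** **Centre.** The only text on centre adjustment is section 5.3 item (6): "Center effects will be adjusted using Cox shared frailty models or generalized estimating equations (GEE) with center as a random effect". It gives no rule for choosing between the two methods, no working correlation and no small-sample correction. Section 5.1 gives the setting: "eight participating centers between January 1, 2001, and December 31, 2023". Section 5.4.2 (2), which sets out the primary analyses, does not mention centre. Section 5.4.2 (5) refers back to 5.3 but lists only the propensity methods and the E-value. RFS, DMFS and OS (section 3.2.1, items 3, 7 and 9) are all times censored at last follow-up.

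**Calendar time.** Section 5.3 item (5) gives the adjustment set: "Multivariable regression models will adjust for known prognostic factors (age, tumor size, pathological grade, margin status, etc". The list is open-ended and does not name year or period of surgery. Section 3.1.2 (2) makes trends in treatment over two decades a secondary objective, and section 5.4.2 (1) uses period for that purpose only: "Distributions and temporal trends (e.g., by 5-year intervals", which "will be described, stratified by pathological grade and time period". The outcome analyses are split by grade alone: "All primary analyses will be stratified by pathological grade (benign/borderline/malignant) to compare prognostic factors across grades". Period is absent from the subgroups and sensitivity analyses. Covariates are chosen by "backward stepwise regression (based on AIC) or LASSO penalized regression (when many variables", with no term forced in.

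**The concern.** GEE deals with clustering through a working correlation and a sandwich variance, and there is no random effect in it to specify. Frailty estimates effects conditional on centre and GEE estimates marginal effects, so an unguided choice between them is also a choice of estimand. The sandwich variance relies on many clusters. With 8, standard errors are too small and confidence intervals too narrow, so weak prognostic factors would be declared independent ones too often.

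Year of surgery raises a question of bias, not precision. If procedure or adjuvant use shifted over the accrual window and recurrence risk or its ascertainment shifted too, leaving year out moves part of the era difference into the treatment coefficient. The planned E-values address unmeasured confounding, whereas year of surgery is measured.

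**Working it through.** **1. The plan's own figure.** Section 5.4.1 expects about 3,500 patients, a grade mix of 7:2:1 and about 11% recurrence, giving about 380 events.
- 3,500 × 0.11 = 385.
- With the grade-specific rates in section 2.2.2: 3,500 × (0.7 × 0.071 + 0.2 × 0.167 + 0.1 × 0.251) = 379.

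Both reproduce the figure. At 10 events per variable, 380 / 10 = 38, inside the stated 30–40. The plan gives no figure for the centre model, so the rest is a separate check.

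**2. Reference distribution.** If a robust statistic from 8 centres behaves like t on 7 df but is compared with 1.96, its true size is 2 × P(t₇ > 1.96) = 0.091. On 6 df it is 0.098.

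**3. Simulated size of a nominal 5% test, null patient-level exposure, 3,500 patients.** Assumed, not from the documents: equal centres, or sizes 1200/900/500/300/250/150/120/80; between-centre SD 0.2–0.4 on the log-odds or log-hazard scale; between-centre SD of exposure 0–1 (logistic) or 0.5–1 (Cox) on the logit scale.

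| Outcome model | Robust z, 8 equal | Robust z, 8 unequal | Centre within the model |
|---|---|---|---|
| Logistic GEE, about 11% events, 2,000 runs per setting | 0.10–0.13 | 0.14–0.17 | 0.04–0.06 (fixed effects) |
| Cox, censored times, about 290–520 events, 1,500 runs per setting | 0.11–0.13 | 0.13–0.17 | 0.04–0.06 (stratified) |

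With 40 equal centres the logistic GEE figure falls to 0.05–0.07, so the small number of centres is the cause. Replacing z by t on 6 df gives 0.04–0.06 with equal centres but 0.07–0.11 with unequal ones, so changing the reference distribution alone is not enough.

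**4. Frailty variance.** A between-centre variance on 7 df has an approximate 95% interval of 7/χ²₀.₉₇₅ to 7/χ²₀.₀₂₅ = 7/16.01 to 7/1.690, or 0.44 to 4.1 times the estimate, before sampling error within centres is added.

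**5. Omitting period: illustration.** Take two equal periods, a true risk ratio of 1, exposure prevalence p₁ then p₂, and late/early risk ratio r. The crude risk ratio is [(p₁ + p₂r)/(p₁ + p₂)] ÷ [((1−p₁) + (1−p₂)r)/(2−p₁−p₂)].
- p₁ = 0.4, p₂ = 0.6, r = 0.85: 0.91 / 0.94 = 0.97.
- p₁ = 0.2, p₂ = 0.8, r = 0.5: 0.60 / 0.90 = 0.67.

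These prevalences and period effects are assumptions. The documents give none.

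**6. What the fix costs.** Accrual from 2001 to 2023 gives five 5-year bands (the last one short), hence four coefficients. Stratifying by centre uses none.
- Whole cohort: 380/34 = 11.2 events per variable with 30 other variables, and 380/44 = 8.6 with 40. Without period these are 12.7 and 9.5.
- Malignant stratum: 350 × 0.251 = 88 recurrences, or 88/8 = 11 per centre if centres were equal.
- Centre crossed with period: 88/40 = 2.2 malignant recurrences per stratum, too sparse to use.

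**The case against.** The best defence is that the sentence is loosely worded. Section 5.4.2 (3) also plans logistic regression, so frailty may be meant for the time-to-event models and GEE for binary ones. That reading is possible and would make deleting GEE everywhere unnecessary. But the text does not say so, the random effect is wrong under either reading, and the few-centres problem applies to binary outcomes as well.

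A reader might infer that no valid centre adjustment is planned, or that frailty fails once procedure choice differs by centre. Neither follows. Shared frailty is a standard model for censored times. Differing procedure mix breaks its assumption only if the mix is correlated with the centre's baseline hazard, and the documents give no data on that. In a gamma-frailty simulation with 8 unequal centres, type I error was 3.8–7.5% without such correlation and 5.1–8.1% with a correlation of 0.5, with log hazard ratio bias of at most 0.04. Stratified or fixed centre effects gave 3.7–5.5%. Stratification is somewhat better, but frailty hazard ratios are not shown to be invalid.

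On calendar time, the open-ended list leaves room for year of surgery, and censored-time methods deal in part with unequal follow-up. Both points stand. They show that adjustment is unspecified, not that it is planned, and AIC or LASSO selection could drop year even if it were offered.

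A reader might also infer from the reference to "the 2019 WHO three-tier classification" that earlier cases were graded on different criteria. The documents do not say that criteria changed in 2019 and give no dates for other editions, so an analysis by edition in force cannot be specified from them.

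**Conclusion.** The point holds in two limited parts.

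First, one of the two permitted centre adjustments is wrong as written and unsuited to the censored primary endpoints. If it were carried out with uncorrected robust z-tests on 8 centres, nominal 5% tests would have a true size of about 10–17%. That range rests on assumed centre sizes and between-centre variation; the 9% from t on 7 df does not depend on those choices. The criticism that 8 centres are too few applies to uncorrected robust errors. For frailty, the shortcoming shown is an imprecise variance.

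Second, year of surgery is not committed to as an adjuster over a 23-year window in which the plan sets out to describe changes in treatment. The risk ratios of 0.97 to 0.67 under a true value of 1 show what could happen. It would be too strong to say that era differences will appear as treatment effects, because the documents give no figures on how either treatment or risk moved.

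Both parts should be settled before the single database lock described in section 6.2.4, so that the handling is not chosen after results are seen.

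**What to change.** - **Time-to-event endpoints:** remove the GEE option. Stratify the Cox baseline hazard by centre, pooling the smallest centres where events are sparse, and keep shared frailty as a sensitivity analysis.
- **Binary outcomes, if GEE is kept:** delete the random-effect wording and specify a small-sample-corrected variance together with a t reference.
- **Year of surgery:** force it into the Cox, Fine-Gray, propensity and imputation models, exempt from AIC or LASSO selection. Use a spline or the 5-year bands as a covariate, and do not cross it with centre as strata.

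No new data are needed: the date of surgery already starts every endpoint clock and centre is known by design. The cost is SAP wording and up to four coefficients. That is minor for the whole cohort but noticeable in the malignant stratum, where 88 recurrences allow about nine terms at 10 events each. A three-knot restricted cubic spline uses 3 − 1 = 2 coefficients and would be the more economical form there. Strata with no exposure contrast contribute nothing, which is the reason to pool the smallest centres.
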